- Anthropometrics & Vital Signs: Body mass and height will be obtained using standardized techniques. In addition, we will also measure waist and hip circumferences using a tape measure. Blood pressure and heart rate will be assessed using standard techniques. If necessary, participants may be provided with a gown. Measures will be taken in duplicate, or triplicate if not within acceptable agreement.
- FibroScan: A FibroScan (FibroScan® 530 Compact, Echosens, Paris, France) will be performed to determine NAFLD status based on Controlled Attenuated Parameter (CAP) score. FibroScan, similar to an ultrasound scan, is a technique to assess liver health. FibroScan is a routinely used clinical tool in most centers to assess liver health. Outcomes of FibroScan are “Controlled Attenuated Parameter (CAP)” and “Transient Elastogram (TE)”. CAP measurement strongly correlates with steatosis, while TE measures the stiffness of the liver as a surrogate marker of fibrosis, as described above. CAP values range from 100 to 400 dB/m, and higher numbers indicate more pronounced steatosis. TE values range from 2.5 kPa to 75 kPa, and higher numbers indicate more pronounced stiffness (fibrosis). Measurement via FibroScan is done when the subject is lying down on his/her back. The test involves a probe being passed over the right upper quadrant of the abdomen to measure the liver fat content and stiffness. The results are then immediately available for review once the scan is complete. No special preparation is required before the FibroScan. We will use the CAP cut-point of 241 dB/m as suggested by Shin et al. to determine baseline steatosis.⁶⁶ A subject with a CAP score of 241 dB/m or greater will be accepted as having steatosis. FibroScan test takes about 20 minutes to complete including the generation and interpretation of the results.

In the rare instance that a valid scan is not feasible, the participant will be accepted as having NAFLD and will be allowed to proceed with the study. If upon initial Magnetic Resonance Imaging (MRI), the participant is found not to have NAFLD, then participation will be discontinued at that time.

Out of the participants whose eligibility is confirmed:

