- *Fibroblast Growth Factor-21: An Adjunct Biomarker for Early Detection of Non-Alcoholic Fatty Liver Disease in Children* (IRB Protocol: 206278): Eighteen subjects, between the ages of 10-17 years completed this study between November 2017 and January 2019, were found to have NAFLD via magnetic resonance imaging. Of these, participants for whom consent was obtained to be contacted for future studies and have their information or samples used for future research may be recruited.
- *Liver Assessment via FibroScan* (IRB protocol: 260576): Participants will be recruited based on their FibroScan results (i.e. CAP score of 241 dB/m or greater). Of these, participants for whom consent was obtained for contact for future research, use of information obtained over the course of this study in future research studies related to liver and/or metabolic health, and use of information obtained over the course of this study for screening purposes for other studies related to liver and/or metabolic health, may be recruited.

Information from the AC medical records regarding a participant's contact information, demographics, and health, including medical history, medical diagnoses, medicines, puberty, date of birth, anthropometrics, vital signs, blood and imaging results, and other test results and labs may be collected upon consent/assent. This information may be collected, retrospectively (i.e., collection of information already present in the medical record at the time of enrollment) and prospectively (i.e., collection of new information that may become available after study enrollment), from the time of study enrollment up to the time that data analysis for this study is complete and results have been published (up to 3 years from enrollment).

Inclusion Criteria for Initial Enrollment:

- Ages 13-18 years (inclusive) for both sexes
- Any ethnic/racial background
- English speaking competence
- Obesity (BMI \geq 95th percentile for age and sex)
- Low risk to participate in an exercise program during initial phone screening
- Late stages of puberty (i.e., Tanner stage IV or V)
 - Female participants should have attained menarche. By definition, onset of menstrual cycles corresponds to a minimum of Tanner stage IV breast development in females. A verbal confirmation of the attainment of menstrual cycles will be enough.

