 - For male participants, a verbal confirmation of late puberty signs (e.g., facial hair growth, deepening of the voice, completed linear growth) will be enough for initial enrollment. However, pubertal assessment will be conducted by the study physician upon consent/assent to confirm late pubertal status (see above).

Inclusion Criteria to Continue in the Study:

- Cleared for physical activity
- Presence of NAFLD as determined by FibroScan CAP score or MRI (see above)
- Confirmed lack of diabetes as determined by OGTT (see above)
- Confirmed late stages of puberty (i.e., Tanner stage IV or V) (see above)
- Confirmed eligibility per medical history (see above)

Exclusion criteria:

- Pre-pubertal or early stages of puberty
- Pregnancy (verbal assessment)
- Confirmed lack of NAFLD in the past 6 months via biopsy, FibroScan or MRI
- Presence of an implantable medical device or metal objects in the body (a contraindication for FibroScan)

- High-risk to participate in an exercise program as determined by “The Physical Activity Readiness Questionnaire for Everyone” (see above)
- Unable to cooperate with study procedures and tests as determined by study PI, including genetic or physical conditions impacting mobility over the past year
- Having known chronic illnesses/disorders that may independently affect study outcome measures: type 1 diabetes mellitus, T2D, neurologic (e.g., epilepsy), developmental (developmental delay, autism spectrum disorder), endocrine (Cushing’s, growth hormone deficiency), hepatic (other than NAFLD), autoimmune, cardiac and renal disorders
- Taking any of the following medications that can affect study outcome at the time of enrollment: insulin, metformin or any other anti-diabetics, antipsychotics, oral steroids, and anabolic drugs (growth hormone replacement therapy, testosterone, and oxandrolone). The participant will not be excluded from the study if he/she begins them during the study unless recommended otherwise by the primary physician.
- Adolescents who have a history of claustrophobia.
- Adolescents who need sedation in order to complete MRI.
- Adolescents determined ineligible by the PI or delegated staff.

Risks and Benefits

Subject Confidentiality: A risk to study participants is the potential for loss of confidentiality of study data. Measures to protect the confidentiality of study data will be implemented as described in the Data Handling and Recordkeeping section below.

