As an exploratory aim, diagnostic performance of FibroScan for the NAFLD adolescent will be determined by discriminating NAFLD status defined by FibroScan against that by MRI to calculate sensitivity, specificity, positive and negative predictive values. Additional agreement statistics such as concordance correlation coefficient and Bland-Altman plots will be provided for the continuous measurements of IHTG levels measured by both methods.

In our pilot data, the IHTG levels were 11.5 ± 5.4 percent at baseline for NAFLD subjects (N=23). With a pre-defined clinically significant change of 20% relative decrease from baseline, we expect the NAFLD subjects' fat percent will be decreased to an average of 9.2 ± 5.4 percent after HIIT intervention, which is an equivalent effect size of 0.43. In order to detect this effect size at 80% power, we will need 38 NAFLD participants in the intervention group, therefore 8 NAFLD subjects in the control group. Accounting for a 20% dropout rate and false-negative screening from FibroScan, we propose to enroll 58 subjects with NAFLD. Therefore, we need to screen no less than 150 subjects at-risk for NAFLD at baseline, to be able to identify 58 subjects with NAFLD (NAFLD prevalence was 40% in our pilot study, see preliminary data section above).

Ethical Considerations

This study will be conducted in accordance with all applicable government regulations and the University of Arkansas for Medical Sciences research policies and procedures. This protocol and any amendments will be submitted and approved by the UAMS Institutional Review Board (IRB) to conduct the study.

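### FibroScan decides who reaches the baseline MRI, so the planned baseline sensitivity, specificity and NPV would reflect the entry rule, not FibroScan's accuracy

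*Combined protocol and SAP*

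**What the plan says.** The Data Analysis section sets an exploratory aim of "discriminating NAFLD status defined by FibroScan against that by MRI to calculate sensitivity, specificity, positive and negative predictive values". It names no visit, no analysis set and no correction for selective use of MRI.

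The entry procedure is spread over several sections:

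- **Study Visit 1, FibroScan:** "A subject with a CAP score of 241 dB/m or greater will be accepted as having steatosis". The procedures that follow are introduced with "Out of the participants whose eligibility is confirmed".
- **Study Visit 1, failed scans:** "In the rare instance that a valid scan is not feasible, the participant will be accepted as having NAFLD" and goes on. The same paragraph adds that if such a participant is "found not to have NAFLD, then participation will be discontinued at that time".
- **Inclusion Criteria to Continue in the Study:** "Presence of NAFLD as determined by FibroScan CAP score or MRI (see above".
- **Magnetic Resonance Imaging (MRI):** the baseline scan precedes the Visit 2 fitness test. A second precedes the 5-week OGTT, and a third, for the exercise group only, precedes the 3-month OGTT.
- **Exclusion criteria:** "Confirmed lack of NAFLD in the past 6 months via biopsy, FibroScan or MRI".
- **Study Population:** recruitment may draw on 18 participants of an earlier study who "were found to have NAFLD via magnetic resonance imaging", and on participants of a FibroScan study chosen because their CAP was already 241 dB/m or more.

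**The concern.** Sensitivity and specificity require the reference test in FibroScan-negatives as well as FibroScan-positives. Here the test under evaluation decides who goes on to the reference test. This is partial-verification bias in its extreme form: almost no one in the negative row has an MRI.

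An analyst following the plan at baseline would report figures fixed by the entry rule. A specificity of 0% would look odd and probably be questioned. A sensitivity near 100% would not, and could be read as support for FibroScan screening of at-risk adolescents. Pooling baseline with follow-up would hide the problem, because the empty cells then fill with scans from participants chosen for a positive CAP.

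PPV survives, with two limits. It depends on a recruited mix that is enriched for known NAFLD and excludes recent known negatives. And if MRI-negative participants who leave the study were also left out of the accuracy set, PPV would be 100% by construction.

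**Working it through.** **The plan's own numbers.** The documents state no accuracy figure. Their screening numbers reproduce: 38 + 8 = 46 completers; 46/0.80 = 57.5, rounded up to 58; 58/0.40 = 145, covered by screening 150 (150 × 0.40 = 60).

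**Inputs.** From the documents: N = 150 and prevalence 40%, so 60 with NAFLD and 90 without. Assumed, because the documents give none: true sensitivity/specificity of 95/70, 90/80 and 85/90%. The counts are upper limits, since some adolescents stop before MRI for other reasons.

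**Full table, had everyone received MRI.** TP = 60 × sensitivity, FN = 60 − TP, TN = 90 × specificity, FP = 90 − TN.

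| Assumed sens/spec | TP | FP | FN | TN | No MRI (FN + TN) | True NPV |
|---|---|---|---|---|---|---|
| 95/70% | 57 | 27 | 3 | 63 | 66 | 63/66 = 95.5% |
| 90/80% | 54 | 18 | 6 | 72 | 78 | 72/78 = 92.3% |
| 85/90% | 51 | 9 | 9 | 81 | 90 | 81/90 = 90.0% |

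**What the gated design yields at baseline.** Let k be the number of CAP-negative, MRI-positive adolescents who enter through the MRI alternative in the continuation criterion.

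- Specificity = 0/(0 + FP) = 0% in all three cases (0/0 if FP = 0).
- NPV = 0/(0 + k): undefined if k = 0, and 0% if k > 0.
- Sensitivity = TP/(TP + k): 100% if k = 0. It falls to the true 95, 90 or 85% only if all 3, 6 or 9 missed cases enter.

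**PPV = TP/(TP + FP), with Clopper-Pearson 95% intervals.**

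| Assumed sens/spec | PPV at 40% prevalence | PPV if all 18 earlier cases join | PPV if MRI-negatives are dropped |
|---|---|---|---|
| 95/70% | 57/84 = 67.9% (56.8–77.6) | 67.26/91.02 = 73.9% | 57/57 = 100% |
| 90/80% | 54/72 = 75.0% (63.4–84.5) | 63.72/79.56 = 80.1% | 54/54 = 100% |
| 85/90% | 51/60 = 85.0% (73.4–92.9) | 60.18/68.10 = 88.4% | 51/51 = 100% |

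The third column is an upper bound that assumes all 18 still have NAFLD: 18 + 132 × 0.40 = 70.8 with NAFLD and 132 × 0.60 = 79.2 without. The number recruited for an earlier positive CAP is not given, so its effect cannot be sized.

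**Follow-up scans.** At 5 weeks, 38/46 = 83% of planned completers are trained; at 3 months all scanned participants are. A simulation shows what pooling baseline and 5-week pairs would do. All its settings are assumptions except the 40% prevalence: a normal model for liver fat, correlation of 0.6 or 0.75 between CAP and liver fat, 30% or 70% of CAP error persistent within a person, a mean fall of 0 or 0.3 SD by 5 weeks, and 48% CAP-positive at baseline.

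| Measure | True baseline value | Pooled, CAP-selected sample |
|---|---|---|
| Sensitivity | 0.73–0.81 | 0.90–0.95 |
| Specificity | 0.69–0.74 | 0.17–0.34 |
| NPV | 0.79–0.85 | 0.62–0.76 |

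The 5-week pairs alone are also distorted: specificity is 0.33–0.58, against 0.69–0.77 in an unselected sample at the same visit.

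**The case against.** The strongest reply is that the gate is inferred. The protocol expressly ends participation for those who fail the exercise-safety and puberty checks, but has no such sentence for a CAP below 241. The continuation criterion also allows entry by MRI. This is true, but the sections point one way: later steps are for confirmed eligibles, no study MRI is described for a valid negative CAP, and the sample-size paragraph itself allows for NAFLD cases missed by FibroScan at screening. If MRI is a second entry route, it admits only MRI-positives, so the true-negative cell stays empty.

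Second, the plan names no visit, and follow-up pairs can fill all four cells. That also stands: the 0% specificity and undefined NPV are baseline results. The follow-up tables, however, do not estimate screening accuracy.

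Third, some FibroScan-negatives might have an MRI in their medical record, which the protocol allows to be collected. No such use is planned, and those scans would be a selected subset.

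Fourth, the sentence discontinuing MRI-negative participants sits in the failed-scan paragraph. Read there, it covers people with no valid CAP, who enter no cell of the table. Its reach is unclear, so a PPV of 100% is a risk to exclude, not a prediction.

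Fifth, the intervals use the full counts and so are the narrowest case. With half as many reaching MRI (an assumption), 27/36 gives 58–88% in place of 63–85%. This affects precision, not the argument.

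**Conclusion.** The concern holds. Under the entry rule as most naturally read, baseline specificity and NPV carry no information, sensitivity is overstated (by 5 to 15 points in the three illustrated cases if no FibroScan-negative enters), and PPV is the only one of the four measures that can be estimated. It applies to the recruited mix alone.

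The results for specificity and NPV do not depend on the assumed accuracy values; the counts and PPVs do. The conclusion rests on reading the continuation criterion as a gate, which the text supports without stating outright. The aim is exploratory and the primary analysis is untouched, so this should be corrected but does not threaten the trial's main conclusion.

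**What to change.** In the exploratory-aim paragraph of the Data Analysis section:

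1. Limit the baseline accuracy analysis to the PPV of a valid CAP of 241 dB/m or more against MRI, with an exact confidence interval.
2. Define the accuracy set as everyone with such a CAP and a baseline MRI. Keep CAP-positive, MRI-negative adolescents in it even if they then leave the study; exclude those with no valid CAP.
3. Describe PPV as applying to the recruited mix, and add a sensitivity analysis without participants recruited because of earlier MRI-found NAFLD or an earlier positive CAP.
4. State that baseline sensitivity, specificity and NPV are not estimable in this design.
5. Report the 5-week and 3-month FibroScan-by-MRI tables descriptively, one visit at a time, labelled as post-enrolment results in a CAP-selected sample.

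The sponsor should also reconcile the Visit 1 text with the continuation criteria: what happens after a valid CAP below 241, when the MRI alternative applies, and whom the discontinuation sentence covers. This review takes no position on what those rules should be.

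The cost is wording only, with no added procedures. The sponsor gives up three baseline measures, and the source-restricted PPV will have a wider interval. If those measures are wanted, MRI in a random fraction of FibroScan-negatives with Begg-Greenes weighting would recover them. At an assumed sensitivity of 0.85 and specificity of 0.75, scanning 25% of about 76 negatives (about 19 scans) gives standard errors of about 0.08 for sensitivity, 0.05 for specificity and 0.07 for NPV. That option needs extra resources and is not required.

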Non-Alcoholic Fatty Liver Disease (NAFLD) is characterized by fatty infiltration (steatosis \geq 5% of liver volume) and is the most common chronic liver disease of childhood. The estimated prevalence of NAFLD is 29% to 38% in obese children¹. NAFLD is rare before puberty, but can be diagnosed during puberty. Routine screening for NAFLD is recommended in at-risk groups and is done via measurement of serum alanine aminotransferase (ALT) level, but this test has a low specificity¹. Using Magnetic Resonance Imaging (MRI), a reference diagnostic test, we demonstrated that 40% of obese children (10-17 years) who attended to our weight management clinic had NAFLD. Twice the sex-specific ALT level, a recommended cut-point for further evaluation¹, had only 30% specificity in our cohort. Further, ALT levels do not correlate with the stage of steatosis or fibrosis.² Recent findings suggest that the degree of hepatic fat content (i.e., Intrahepatic triglyceride [IHTG] percent) in patients with NAFLD plays an independent role in progression of disease to advanced characterized by inflammation (Non-Alcoholic Steatohepatitis [NASH]) and fibrosis^{3,4}. This notion is supported by the finding that among adult NAFLD patients with no baseline fibrosis, those with a higher baseline IHTG (\geq 15.7%) developed fibrosis at a much higher rate (OR 6.67, 95% CI:1.01-44.1, $p < 0.05$) after a 1.75 year follow up⁵.

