Participants can bring a friend or family member to workout with them if they would like. A separate release will be signed by the friend or family member in order to workout at the ACNC fitness facility.

5-Week/Post-Intervention: All Subjects

Study Visit 3 – This visit may last up to 3 hours and include: measurement of body mass and height, FMD, pregnancy screening (if female), DXA, and fitness test as described above. Participants who are in the control group will complete this visit 5 weeks \pm 1.5 week after study visit 2. Participants will be reimbursed for their time with \$25 at the end of the visit.

Study Visit 4 – This visit may last up to 4 hours and include: measurement of body mass and height, vital signs, OGTT, FibroScan, urine collection, and dietary questionnaire as described above. Participants will be reimbursed for their time with \$50 at the end of the visit.

3-Month Follow-up: Exercise Group Only

Study Visit 5 – Participants from the exercise group will be asked to attend a follow-up visit 3 months \pm 2 week after last HIIT session. This visit may last up to 4 hours and include: measurement of body mass and height, hip and waist circumference, vital signs, pregnancy screening (if female), DXA, FibroScan, FMD, OGTT, urine collection, and dietary questionnaire as described above. FMD, pregnancy screening (if female) and DXA will only be completed in the instance that this visit takes place at ACNC. Participants will be reimbursed for their time with \$50 at the end of the visit.

Magnetic Resonance Imaging (MRI)

In addition to the study procedures described above, all participants will complete a MRI scan before the baseline/pre-intervention fitness test, and another MRI scan before the 5-week/post-intervention OGTT. Furthermore, participants in the exercise group will complete an additional MRI scan before the 3-month follow-up OGTT. The MRI scans will be done at the Arkansas Children's Hospital Radiology Department for the determination of hepatic fat content via magnetic resonance imaging. Each visit for completion of a MRI scan will last up to 1.5 hours. Participants will be reimbursed for their time with \$50 after each visit.

Physical Activity Assessment

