Samples will be stored in freezers in the Arkansas Children's Nutrition Center and/or Arkansas Children's Research Institute. The freezers are constantly monitored to ensure that the proper temperature is maintained. Samples will be identified using the subject's unique study acronym along with the date of sample collection and type of sample (e.g. EDTA plasma, serum). Remaining samples may be stored indefinitely or until used up for future analyses. If consented, samples may be used in future studies related liver and/or metabolic health. Participants and/or parents may contact the study's principal investigator, if they choose to withdraw consent to use samples and/or information in future research. In this case, a written letter addressed to the principal investigator expressing their desire to withdraw their consent would be required. If the information and/or samples have been shared or if publication of results has occurred, then we may not be able to remove information and/or samples.

Data Analysis

Exploratory data analysis will be conducted prior to formal statistical analysis. We will examine the distributions of all key variables to check for data errors and ensure that modeling assumptions are not violated. Numerical summaries including means, standard deviations, medians and histogram graphical techniques will be used for continuous variables and frequencies will be computed for categorical variables. For both aims, the primary outcome is IHTG level measured by both FibroScan and MRI, and secondary outcomes are fitness level, and various cardiometabolic disease markers (i.e.; insulin, glucose, adiponectin, etc.). The immediate (Aim 1) and sustained (Aim 2) effect of HIIT will be measured by comparing the changes in outcomes between groups using a linear mixed-effect framework with a subject-level random intercept. Changes in the outcomes are defined as difference between follow up visits (5-week and 3-month) versus the baseline. The independent variables will be group (intervention vs control), visit time (baseline, 5-week, 3-month) and their interaction term. This model specification can test the effect of intervention as well as difference between visits, while correctly account for the within-subject correlation due to repeated visits. Post-hoc contrasts of visit time between 5-week and baseline will be used to test the hypotheses under Aim 1, while contrasts between 3-month and 5-week will be used to test the hypotheses under Aim 2.

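### The planned concordance coefficient and Bland-Altman plots need FibroScan and MRI on one scale, but CAP is in dB/m, MRI fat is in percent, and no conversion is given

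*Combined protocol and SAP*

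**What the plan says.** The last part of the Data Analysis section sets an exploratory aim on the diagnostic performance of FibroScan. NAFLD status by FibroScan is compared with status by MRI through sensitivity, specificity and predictive values. It then adds, as examples of further agreement statistics, that "concordance correlation coefficient and Bland-Altman plots will be provided for the continuous measurements of IHTG levels measured by both methods".

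The same section names both devices for the main endpoint: "the primary outcome is IHTG level measured by both FibroScan and MRI".

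The FibroScan item under Study Visit 1 describes what the device delivers. There are two outputs: "CAP measurement strongly correlates with steatosis, while TE measures the stiffness of the liver as a surrogate marker of fibrosis". On the scale it says "CAP values range from 100 to 400 dB/m, and higher numbers indicate more pronounced steatosis", and on the cut-point "A subject with a CAP score of 241 dB/m or greater will be accepted as having steatosis". TE is in kPa.

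The MRI section says the scans are done "for the determination of hepatic fat content via magnetic resonance imaging". IHTG is expressed as a percent in the background, in the Preliminary Results table and in the sample-size paragraph, which gives 11.5 ± 5.4 percent for pilot subjects with NAFLD. The documents contain no equation, calibration or standardisation that turns CAP into percent fat.

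**The concern.** The CCC and the Bland-Altman plot both ask whether two methods return the same number for the same person. The CCC falls with any difference in mean or spread between the methods, however well one predicts the other. A Bland-Altman difference has meaning only when both readings share a unit.

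The text treats both devices as producing continuous IHTG levels, but only MRI does so here. If CAP is entered in dB/m, the CCC mostly reports the distance between the two scales and cannot separate a FibroScan that follows liver fat closely from one that does not. If a conversion is used instead, the plan does not say which, and the CCC then depends on a choice that could be made after the data are seen. At stake is the only continuous comparison of the two devices that the plan names.

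**Working it through.** The documents give no figure for this analysis, so there is nothing to reproduce. The check asks what the CCC and Bland-Altman statistics would be if CAP is used as recorded.

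**Inputs**
- MRI IHTG: mean 11.5, SD 5.4 percent (Data Analysis, sample-size paragraph). The Preliminary Results table gives 11 ± 5.4, which makes no material difference (see below).
- CAP scale 100 to 400 dB/m, cut-point 241 dB/m (Study Visit 1, FibroScan).
- CAP mean and SD are not in the documents. Assumed here: mean 260 to 320, SD 30 to 45 dB/m.

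**CCC**

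CCC = 2·r·s1·s2 / (s1² + s2² + (m1 − m2)²), with m1 = 11.5 and s1 = 5.4.

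For CAP 290 ± 40 and r = 1:
- numerator 2 × 5.4 × 40 = 432
- denominator 29.16 + 1600 + 278.5² = 29.16 + 1600 + 77562.25 = 79191.41
- CCC = 432 / 79191.41 = 0.0055

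The CCC is proportional to r, so it is 0.0038 at r = 0.7 and 0.0027 at r = 0.5. With an MRI mean of 11 instead of 11.5, the r = 1 value is 432 / (29.16 + 1600 + 279²) = 432 / 79470.16 = 0.0054.

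Within the assumed range the CCC rises with the CAP SD and falls with the CAP mean, so the extremes lie at two corners:

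| CAP mean, SD | Denominator | r = 0.5 | r = 0.7 | r = 1 |
|---|---|---|---|---|
| 320, 30 | 29.16 + 900 + 308.5² = 96101.41 | 0.0017 | 0.0024 | 0.0034 |
| 260, 45 | 29.16 + 2025 + 248.5² = 63806.41 | 0.0038 | 0.0053 | 0.0076 |

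The range is therefore 0.0017 to 0.0053 for r between 0.5 and 0.7, and 0.0034 to 0.0076 under perfect tracking.

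**Bound that does not rest on the assumed CAP mean and SD**

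A variable confined to [lo, hi] with mean m has SD at most √((m − lo)(hi − m)). Setting r = 1 and searching over all means and feasible SDs:
- CAP confined to 241–400: maximum at mean 282, SD 69.6. CCC = 2 × 5.4 × 69.556 / (29.16 + 4838 + 270.5²) = 751.2 / 78037.4 = 0.0096.
- CAP anywhere on 100–400: maximum at mean 115, SD 65.4. CCC = 2 × 5.4 × 65.383 / (29.16 + 4275 + 103.5²) = 706.1 / 15016.4 = 0.047.

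The first bound suits baseline, where a valid scan must reach 241. The second also covers follow-up, where CAP may fall below 241.

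**Bland-Altman**

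With CAP 290 ± 40 and perfect tracking, the mean difference is 290 − 11.5 = 278.5. The SD of the differences is 40 − 5.4 = 34.6, so the limits are 278.5 ± 1.96 × 34.6, about 211 to 346. The unit is neither dB/m nor percent. The differences correlate 1.0 with the pairwise means, so the pattern comes entirely from the scales.

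**On a common scale**

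If CAP is first converted to percent, perfect tracking gives a CCC of 1.00. At r = 0.7 it is 0.70 when the conversion matches mean and SD. It is 2r²/(1 + r²) = 0.98 / 1.49 = 0.66 when the conversion is a regression prediction. On the raw scales at CAP 290 ± 40 it is 0.0038.

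**The case against.** The plan does not say that CAP in dB/m will be entered. It speaks of IHTG levels by both methods, and the analyst may intend a conversion. That is fair, and a reader should not infer that a raw-unit analysis is stated policy. What stands is that no conversion is described, so the analysis is either on unlike scales or not specified. Either reading needs a change to the text.

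The two statistics are offered as examples, so correlation or regression is not ruled out. That also stands, but the two methods that are named are the ones that do not suit the data.

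A reader might infer that the whole exploratory aim would show no agreement. The documents do not support this. Its stated content is diagnostic performance, and sensitivity, specificity and predictive values use dichotomised status, which units do not touch. Nor would the Bland-Altman plot show near-zero agreement. That phrase fits only the CCC. The plot yields a bias and limits that have no meaning, and a bias near 280 would be noticed at once, which lowers the risk of a misleading report.

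Finally, the documents nowhere set a question about whether change in CAP follows change in MRI fat. Analysing change would be an addition, not a correction.

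**Conclusion.** The point holds, with a narrow reach. The two named statistics do not suit the two measurements as the protocol describes them. Applied to CAP as recorded, the CCC would be 0.0017 to 0.0053 at correlations of 0.5 to 0.7 and 0.0034 to 0.0076 at a correlation of 1, for an assumed CAP mean of 260 to 320 and SD of 30 to 45. The conclusion does not depend on those assumptions: at the documented MRI mean and SD, the ceiling is about 0.0096 for CAP on 241–400 and about 0.047 on 100–400. The Bland-Altman plot would be uninterpretable.

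The damage is confined to the supplementary continuous agreement statistics. It is tempting to read the mismatch into the main results because both devices are named for the primary outcome. The documents do not support that: the Aim 1 and Aim 2 contrasts compare visits and groups and do not use the agreement statistics. This should be corrected, but it changes no confirmatory test, sample size or eligibility rule.

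**What to change.** In the exploratory paragraph of Data Analysis, replace the CCC and Bland-Altman sentence with:

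- A Spearman or Pearson correlation of CAP with MRI IHTG, with 95% CI, at each visit where both are measured.
- A regression of MRI IHTG (percent) on CAP (dB/m).
- Optionally, the correlation of the baseline-to-5-week changes in CAP and MRI IHTG.

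State that, apart from invalid scans, continuing in the study requires CAP of at least 241 dB/m. This truncates baseline CAP and will tend to attenuate the baseline correlation.

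Keep CCC or Bland-Altman only for CAP values converted to percent by a calibration specified in advance. If the calibration is fitted in the same data, label it so and note that the mean bias is then zero by construction and cannot count as evidence of agreement.

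The cost is a few sentences. FibroScan and MRI are already scheduled at baseline and 5 weeks for everyone and at 3 months for the exercise group, so no new data, visits or participants are needed.
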